## **3.2 Exclusion Criteria**

**3.2.1** Prior Therapy

- ❖ Exposure to chemotherapy or radiotherapy within 2 weeks prior to entering the study or those who have not recovered from adverse events due to agents administered more than 2 weeks earlier.
- ❖ Systemic steroids that have not been stabilized ( $\geq 5$  days) to the equivalent of  $\leq 10$  mg/day prednisone prior to the start of the study drugs.
- ❖ No other concurrent investigational agents are allowed.

**3.2.3** History of allergic reactions to Oral 5-azacitidine or Romidepsin.

**3.2.4** Uncontrolled intercurrent illness including, but not limited to, ongoing or active infection, symptomatic congestive heart failure, unstable angina pectoris, cardiac arrhythmia, or psychiatric illness/social situations that would limit compliance with study requirements.

**3.2.5** Pregnant women

**3.2.6** Nursing women

**3.2.7** Active concurrent malignancy (except non-melanoma skin cancer or carcinoma *in situ* of the cervix). Patients whose lymphoma has transformed from a less aggressive histology remain eligible.

**3.2.8** Patients known to be Human Immunodeficiency Virus (HIV)-positive

**3.2.9** Patients with active hepatitis A, hepatitis B, or hepatitis C infection.

**3.2.10** Concomitant use of CYP3A4 inhibitors (see Appendix 2)

**3.2.11** Any known cardiac abnormalities such as:

- Congenital long QT syndrome
- QTc interval  $\geq 500$  milliseconds;
- Patients taking drugs leading to significant QT prolongation (See Appendix 1: Medications That May Cause QTc Prolongation)
- Myocardial infarction within 6 months of C1D1. [Subjects with a history of myocardial infarction between 6 and 12 months prior to C1D1 who are asymptomatic and have had a negative cardiac

risk assessment (treadmill stress test, nuclear medicine stress test, or stress echocardiogram) since the event, may participate];

- Other significant ECG abnormalities including 2nd degree atrio-ventricular (AV) block type II, 3rd degree AV block, or bradycardia (ventricular rate less than 50 beats/min);
- Symptomatic coronary artery disease (CAD), *e.g.*, angina Canadian Class II-IV (see Appendix 3) In any patient in whom there is doubt, the patient should have a stress imaging study and, if abnormal, angiography to define whether or not CAD is present;
- An ECG recorded at screening showing evidence of cardiac ischemia (ST depression of  $\geq 2$  mm, measured from isoelectric line to the ST segment). If in any doubt, the patient should have a stress imaging study and, if abnormal, angiography to define whether or not CAD is present;
- Congestive heart failure (CHF) that meets New York Heart Association (NYHA) Class II to IV definitions (see Appendix 4) and/or ejection fraction  $<40\%$  by MUGA scan or  $<50\%$  by echocardiogram and/or MRI;
- A known history of sustained ventricular tachycardia (VT), ventricular fibrillation (VF), Torsade de Pointes, or cardiac arrest unless currently addressed with an automatic implantable cardioverter defibrillator (AICD);
- Hypertrophic cardiomegaly or restrictive cardiomyopathy from prior treatment or other causes;
- Uncontrolled hypertension, *i.e.*, blood pressure (BP) of  $\geq 160/95$ ; patients who have a history of hypertension controlled by medication must be on a stable dose (for at least one month) and meet all other inclusion criteria; or
- Any cardiac arrhythmia requiring an anti-arrhythmic medication (excluding stable doses of beta-blockers)

### **3.3 Inclusion of Women and Minorities**

Both men and women of all races and ethnic groups are eligible for this trial.

## **4. REGISTRATION PROCEDURES**

### **4.1 General Guidelines**

Eligible patients will be enrolled on study by the study team.

Following enrollment, patients should begin protocol treatment within 14 days. Issues that would cause treatment delays should be discussed with the Principal Investigator. If a patient does not receive protocol therapy within 14 days of enrollment, the patient's enrollment on the study may be canceled, at the discretion of the PI.

### **4.2 Screening**

All potential study patients will be screened and eligibility determined prior to enrollment. Unless otherwise specified, the following procedures and evaluations will be performed as noted in the study calendar (Section 10) prior to the start of study drugs (cycle 1, dose 1):

- 1) Obtain written informed consent and privacy authorization prior to initiating any protocol-required procedure that is not considered standard of care (See Section 4.3)

- 2) Review eligibility criteria
- 3) Review medical chart for past medical/surgical history
- 4) Record medications and prior treatment regiments
- 5) Record response to prior treatment regimen(s)
- 6) Document histopathology from:
  - (i) Original diagnosis
  - (ii) Tumor biopsy in the relapsed setting (if applicable)
- 7) Documentation of known measurable disease parameters by the following procedures:
  - CT of neck, chest, abdomen, and pelvis (PET/CT optional)
  - Skin exam
  - Other imaging techniques documenting disease site other than neck, chest, abdomen, and pelvis, if applicable
- 8) Obtain a 12-lead electrocardiogram (ECG) and calculate the QTc interval.
- 9) Perform a comprehensive physical examination
- 10) Assess and record ECOG Performance Status
- 11) Local laboratory: Collect blood for hematology (CBC with differential counts), chemistry (Na, K, Cl, HCO3, BUN, creatinine, glucose, calcium, magnesium, including serum  $\beta$ -human chorionic gonadotropin [ $\beta$ -hCG] pregnancy test for women who are not postmenopausal or surgically sterile [within 7 days prior to cycle 1, dose 1 and again within 24 hours prior to first dose of the study drugs.]), liver function tests (total protein, Albumin, AST, ALT, total bilirubin, direct bilirubin, alkaline phosphate).
- 12) Calculate creatinine clearance using the glomerular filtration rate (GFR) according to the Cockcroft and Gault Equation, only if screening serum creatinine is > 1.5 mg/dL:  $GFR^* = (140 - \text{age [years]}) \times \text{actual body weight (kg)} / 72 \times \text{serum creatinine}$   
 \*For female patients, multiply by 0.85
- 13) For Exploratory Cohort Only: A lymph node, core-needle biopsy, or bone marrow biopsy will be performed during the screening period for evaluation of gene expression profiling .

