### 3. PATIENT SELECTION

#### 3.1 Inclusion Criteria for Lymphoma

**3.1.1** Phase I: Patients must have histologically confirmed relapsed or refractory non-Hodgkin lymphoma or Hodgkin lymphoma (WHO criteria), with no accepted curative options.

Phase II: Patients with untreated, relapsed or refractory T-cell lymphoma, including patients with central nervous system (CNS) involvement or lymphomatous meningitis are allowed on study.

**Exploratory Cohort:** Patients with histologically confirmed relapsed or refractory Germinal Center (GC)-derived B-Cell Lymphoma (diffuse large B-cell (DLBCL) and follicular lymphoma (FL)) defined by the WHO and Hans criteria with no accepted curative options. (Appendix 5)

**3.1.2.** There is no upper limit for the number of prior therapies. Patients may have relapsed after prior autologous or allogeneic stem cell transplant.

**3.1.3** Evaluable Disease in the Phase I, and measurable disease as defined in Section 11.1 for the Phase II.

**3.1.4** Age  $\geq 18$  years.

**3.1.5** ECOG performance status  $\leq 2$

**3.1.6** Patients must have adequate organ and marrow function as defined below:

- absolute neutrophil count  $\geq 1,000/\text{dL}$
- platelets  $\geq 75,000$  total ( $\geq 50,000$  if bone marrow involvement)
- bilirubin  $\leq 1.5X$  institutional limits
- AST(SGOT)/ALT(SGPT)  $\leq 2.0X$  institutional upper limit of normal
- Serum creatinine within normal institutional limits

OR

- Creatinine clearance  $\geq 50 \text{ mL/min}$  for patients with creatinine levels above institutional normal.

**3.1.7** Negative urine or serum pregnancy test for females of childbearing potential

**3.1.8** All females of childbearing potential must use an effective barrier method of contraception (either an IUDC or double barrier method using condoms or a diaphragm plus spermicide) during the

treatment period and for at least 1 month thereafter. Male subjects should use a barrier method of contraception during the treatment period and for at least 3 months thereafter. Female subjects should avoid the use of estrogen-containing contraceptives, since Romidepsin may reduce the effectiveness of estrogen-containing contraceptives.

**3.1.9** Ability to understand and the willingness to sign a written informed consent document.

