#### **4.4 Registration Process**

To register a patient, the following documents should be completed by a member of the research staff and delivered to the study coordinator:

- Eligibility Screening Worksheet
- Copy of required laboratory and imaging tests
- Signed patient consent forms
- HIPAA authorization form

The Study Coordinator will verify eligibility. To complete the registration process, the Coordinator will:

- Assign a patient study number
- Register the patient on the study
- Confirm registration with the principal investigator

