## 10. STUDY CALENDAR

Baseline evaluations are to be conducted as indicated in the table below, prior to start of protocol therapy. Scans must be done  $\leq$ 4 weeks prior to the start of therapy. In the event that the patient's condition is deteriorating, laboratory evaluations should be repeated within 48 hours prior to initiation of the next

cycle of therapy.

Cycle	Screening	1				2- onward				End of treatment	End of Study (4 weeks after last dose)	Follow-up j
		Day 1	Day 8	Day 15	Day 22	Day 1	Day 8	Day 15	Day 22			
Eligibility & Safety Monitoring												
Informed Consent	X c											
Demographics	X c											
Medical History	X c											
Concurrent Medications	X f	X g	X	X	X	X	X	X	X	X	X	X
Physical exam	X f	X g	X	X	X	X				X	X	X
Vital Signs, weight	X f	X	X	X	X	X				X	X	X
Performance Status	X f	X	X	X	X	X				X	X	X
CBC w/ differential	X f	X g	X	X	X	X	X	X	X	X	X	X
Chemistries a, i	X f	X g				X				X	X	X
EKG	X c		X				X			X	X	
Toxicity Assessment			X	X	X	X				X	X	X
Serum β-hCG	X f											
Urinalysis	X c	X g										
Creatinine clearance	X											
Drug Dispensation												
Oral 5-azacitidine		X				X						
Romidepsin			X	X	X		X	X	X			
Efficacy Measurements												
CT (PET/CT optional)	X c						X b					
Brain MRI	X c, l											
Bone Marrow Biopsy k	X									X c		
Lymph Node Assessment	X c											
PK/Biomarkers												
Lymph Node Biopsy, FNA, or Bone Marrow Biopsy (Optional)	X c		X l									
PK		X d	X d			X						
Correlative Blood Sample		X h										

a) Chemistries include: Chem \*, Mg+, K+, Creatinine, Hepatic Function Panel (LFTs, bilirubin), and LDH. On romidepsin days of cycles 2 and onward, full chemistries may be drawn, but only K+ and Mg+ are required.  
b) CT to occur after cycle 2 and 6, Then CT q3-6 months, until disease progression or initiation of new therapy at the discretion of the Investigator. (PET/CT is optional)  
c) Bone Marrow biopsy will be required after cycle 2 for patients with bone marrow involvement at baseline who have a complete response by imaging and physical exam  

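### Section 4.2 item 12 calculates creatinine clearance only above 1.5 mg/dL, while 3.1.6 needs it for any patient above the institutional normal limit

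*Combined protocol and SAP*

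**What the plan says.** Section 3.1.6 sets renal eligibility by two alternatives. The first is "Serum creatinine within normal institutional limits". The second is a creatinine clearance of at least 50 mL/min, which applies "for patients with creatinine levels above institutional normal". The dividing line is therefore the laboratory's own limit, and the protocol gives no number for it.

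Section 4.2 item 12 gives the Cockcroft-Gault equation and says to use it "only if screening serum creatinine is > 1.5 mg/dL". Here the dividing line is a fixed number.

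The Section 10 calendar has a row for "Creatinine clearance", marked at screening with no footnote. The calendar is introduced with "Baseline evaluations are to be conducted as indicated in the table below". Section 4.2 opens its own list with "Unless otherwise specified, the following procedures and evaluations will be performed as noted in the study calendar".

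Two steps check eligibility before treatment. Section 4.2 item 2 is "Review eligibility criteria", and Section 4.4 states "The Study Coordinator will verify eligibility".

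**The concern.** The eligibility rule and the screening procedure that should serve it use different triggers. If the institutional upper limit is below 1.5 mg/dL, some patients have a creatinine above normal but not above 1.5. Section 3.1.6 judges them by their clearance, and item 12 tells staff not to calculate it.

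What is at stake is whether the renal entry rule is applied as written. The error could go either way: a patient with clearance below 50 mL/min could be registered, or a patient with adequate clearance could be treated as meeting neither route. The rule has a purpose here. Section 2.2.3 describes urinary excretion as the main route of elimination for azacitidine and its metabolites, and Section 7.2.1 reports severe renal tubular dysfunction.

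**Working it through.** There is no trial figure to reproduce. The check compares the two triggers and then asks whether the uncalculated value could matter.

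**Step 1: where the triggers differ.** Let L be the institutional upper limit for creatinine, in mg/dL (not stated).

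- Section 3.1.6 needs clearance when creatinine is above L.
- Section 4.2 item 12 calculates it when creatinine is above 1.5.
- The gap is creatinine above L and up to and including 1.5. It exists if L is below 1.5 and is empty if L is 1.5 or higher.

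**Step 2: can the missing value decide eligibility?** I read the equation in item 12 as

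clearance = (140 − age) × weight / (72 × creatinine), multiplied by 0.85 for women.

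The 50 mL/min threshold comes from 3.1.6. Age 51 is the Phase I median and age 70 lies within the Phase I range of 23 to 79 (Section 2.4.2). The weights of 60 and 70 kg are my assumptions.

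Creatinine 1.5 (in the gap for any L below 1.5); 72 × 1.5 = 108:

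- man, 70 y, 70 kg: 70 × 70 / 108 = 45.4
- woman, 70 y, 60 kg: 70 × 60 / 108 × 0.85 = 33.1
- woman, 51 y, 70 kg: 89 × 70 / 108 × 0.85 = 49.0
- man, 51 y, 70 kg: 89 × 70 / 108 = 57.7

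Creatinine 1.4 (in the gap for any L below 1.4); 72 × 1.4 = 100.8. The same four patients, in order: 48.6, 35.4, 52.5 and 61.8.

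Creatinine 1.2 (in the gap only if L is below 1.2); 72 × 1.2 = 86.4. The same four: 56.7, 41.3, 61.3 and 72.1.

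Of these four, one reaches 50 at creatinine 1.5, two at 1.4 and three at 1.2.

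**Step 3: the age at which clearance crosses 50, at 70 kg.** Setting clearance to 50 gives age = 140 − 50 × 72 × creatinine / 70, with 70 replaced by 70 × 0.85 for women.

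- Creatinine 1.5: 140 − 50 × 108 / 70 = 62.9 for men; 140 − 50 × 108 / 59.5 = 49.2 for women.
- Creatinine 1.4: 140 − 50 × 100.8 / 70 = 68.0 for men; 140 − 50 × 100.8 / 59.5 = 55.3 for women.

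These ages fall inside the Phase I range, so within the gap the result can be on either side of 50.

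**Step 4: would a later step supply the value?** The renal criteria before each treatment in Section 5.1.3 do not apply to Cycle 1 Day 1. After that they accept creatinine up to 2.0 times the upper limit, or no higher than baseline, as alternatives to clearance. A patient slightly above normal passes without a clearance, so these criteria do not fill the gap at entry.

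**The case against.** The strongest reply is that 3.1.6 is the governing criterion and item 12 does not waive it. A patient above normal with no clearance value has met neither route and is not eligible. Item 2 of Section 4.2 and the worksheet and coordinator's check in Section 4.4 apply 3.1.6, and age, weight and creatinine are already on file. Item 12 does not forbid using the equation to settle 3.1.6. All of this stands, and it keeps the point small. It does not remove the mismatch: the check depends on someone noticing that the screening instruction is narrower than the criterion.

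A second reply is that the institutional limit may be 1.5 mg/dL or higher. If so, there is no gap. The documents do not settle this, so the point is conditional.

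A reader might also infer that the calendar is a third conflicting rule, requiring clearance for every patient. The documents do not support that. Section 4.2 defers to the calendar "Unless otherwise specified, the following procedures and evaluations will be performed as noted in the study calendar", and item 12 can be read as just such a specification. The calendar also leaves out patient conditions elsewhere: its β-hCG row carries only a timing footnote, while Section 4.2 item 11 limits the test to women who are not postmenopausal or surgically sterile. The calendar is unclear on this row, and no more than that. If item 12 does override it, the calendar cannot be relied on to supply the missing value.

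Nor is there support for the idea that different sites would apply different rules. Section 13.1 describes Phase I as a single-institution study, and nothing in the documents shows several sites.

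**Conclusion.** The mismatch between item 12 and 3.1.6 is in the text. Whether it has any practical effect depends on the institutional upper limit being below 1.5 mg/dL, which the documents do not state. Where it is, screening as written omits a value that can decide eligibility: at creatinine 1.5 the four illustrative patients run from 33.1 to 57.7 mL/min around a threshold of 50. The illustration rests on assumed weights, and fewer of the four fall below 50 at lower creatinine values. How many patients would be affected cannot be estimated.

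It would go too far to conclude that ineligible patients will be enrolled, since 3.1.6 still applies and Section 4.4 may catch the omission. The point also has no bearing on the response-rate analysis, the two-stage design or its error rates. It is a minor inconsistency in a safety entry rule, worth correcting because the correction is so simple.

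**What to change.** In Section 4.2 item 12, replace "only if screening serum creatinine is > 1.5 mg/dL" with: if screening serum creatinine is above the institutional upper limit of normal. Calculating clearance for all patients would serve equally well. Add a footnote to the creatinine clearance row of the Section 10 calendar stating whichever rule is chosen.

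The cost is one phrase and one footnote. Creatinine and weight are already collected at screening and age is known from eligibility, so no new test is needed.

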#### **4.3 Informed Consent**

##### **4.3.1 Study Informed Consent**

Study personnel must obtain documented consent from each potential patient prior to entering in a clinical study. Consent must be documented on the IRB approved consent form by obtaining the dated signature both of the patient and of the investigator conducting the consent discussion. If the patient is unable sign the consent form, then oral consent, attested to by the dated signature of an impartial witness (someone not involved with the conduct of the study), is the required alternative.

If the patient is illiterate, an impartial witness should be present during the entire informed consent reading and discussion. Afterward, the patient should sign and date the informed consent, if capable. The impartial witness should also sign and date the informed consent along with the individual who read and discussed the informed consent (i.e., study staff personnel).

The information from the consent form should be translated and communicated to the subject in language understandable to the subject. Consent forms will be available in English and Spanish. When the study participant is non-English and non-Spanish speaking, the consent form must be read accurately in its entirety by a qualified professional translator. The translator will provide a written statement indicating that the consent form has been accurately translated from the accompanying English version, and that the study participant consents to participation. The professional translator will sign the consent form as an impartial witness.

A copy of the signed and dated consent form should be given to the patient before participation in the study.

Patients may undergo study screening tests prior to giving written informed consent provided that these tests are considered part of standard care.

The initial informed consent form and any subsequent revised written informed consent form, and written information will receive the IRB approval. The patient or his/her legally acceptable representative will be informed in a timely manner if new information becomes available that may be relevant to the patient's willingness to continue participation in the trial. The communication of this information will be documented.

#### **4.3.2 Consent and Use of Tissue Specimens for Research**

Patients who choose to participate in the optional biopsies will undergo a tissue biopsy pretreatment and a second biopsy between Day 8 and 21 of cycle 1. The investigator or designee is responsible for explaining and verifying the subject's consent before obtaining any biopsy. It will be explained to the patient that allowing the lymph node sample is encouraged, but optional, and participation in the associated clinical study is not dependent upon giving this sample.

#### **4.4 Registration Process**

To register a patient, the following documents should be completed by a member of the research staff and delivered to the study coordinator:

- Eligibility Screening Worksheet
- Copy of required laboratory and imaging tests
- Signed patient consent forms
- HIPAA authorization form

The Study Coordinator will verify eligibility. To complete the registration process, the Coordinator will:

- Assign a patient study number
- Register the patient on the study
- Confirm registration with the principal investigator

## 5. TREATMENT PLAN

### 5.1 Agent Administration

#### 5.1.1 Dose Escalation Scheme

Cohorts of 3 patients will be administered oral 5-azacitidine and romidepsin starting at a dose of 100 mg for oral 5-azacitidine and 10 mg/m^2 for romidepsin. Dose escalations will then commence for each agent individually with a maximum oral 5-azacitidine dose of 300 mg and a romidepsin dose of 14 mg/m^2 representing the highest dose cohort. The dose levels to be considered are outlined in the escalation schema in Table 2. The rules for dose escalation or de-escalation are outlined in table 3.

**Table 1: Regimen Description**

REGIMENT DESCRIPTION					
Agent	Premedications; Precautions	Dose	Route	Schedule	Cycle Length
Oral 5-azacitidine	Anitemeti	300 mg (flat dose)	PO	Days 1-14	35 days
Romidepsin	Antiemeti	14 mg/m 	IV over 4 hours (Administered first during cycle 1)	Days 8, 15, 22 (+/- D 22)	
** Doses as appropriate for assigned dose level.					

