**Figure 1a: Drug Administration and Pharmacokinetic Sampling Schedule (Day 8)**

**Figure 1b: Drug Administration and Pharmacodynamic Sampling Schedule**

**SCHEMA**

**Table 1: Regimen Description**

REGIMENT DESCRIPTION					
Agent	Premedications; Precautions	Dose	Route	Schedule	Cycle Length
Oral 5-azacitidine	Standard Premedications	300 mg (flat dose)	PO Days 1-14	Days 1-14	35 days
Romidepsin	Antiemetic	14 mg/m 	IV over 4 hours	Days 8, 15 and 22	
** Doses as appropriate for assigned dose level.					

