## A. Schema Phase II and Exploratory Cohort

- Oral 5-azacitidine and romidepsin administered at the MTD of the combination to patients with T-Cell Lymphoma: oral 5-azacytidine at 300 mg (flat dose) Days 1-14 and romidepsin 14 mg/m^2 on Days 8, 15 and 22 on a 35 day cycle.
- For Exploratory Cohort Only: Lymph node biopsy for determination of gene expression profile

### CYCLE 1

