**Table 2: Dose Escalation Scheme for the Combination of Oral 5-azacitidine and Romidepsin**

Dose Level	Dose Escalation Schedule		Cycle Length
	Oral 5-azacitidine (Flat dose [mg])	Romidepsin (mg/m  rounded to 14mg/m  )	
Level -1	100 (Days 1-14)	10 (Day 8)	28
Level 1	100 (Days 1-14)	10 (D8 & 15)	28
Level 2	200 (Days 1-14)	10 (Day 8 & 15)	28
Level 3	300 (Days 1-14)	10 (Day 8 & 15)	28
Level 4	300 (Days 1-14)	14 (day 8 & 15)	28
Level 5	300 (days 1-14)	14 (Days 8, 15 and 22)	35
Level 6	300 Days (1-21)	14 (Days 8, 15, 22)	35

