### 5.1.2 Regimen Description (Phase 2)

Treatment will be administered on an outpatient basis. Patients will be treated with oral 5-azacytidine and romidepsin at the MTD (i.e the Recommended Phase 2 Dose, or RP2D). The treatment will be administered as follows: oral 5-azacytidine 300 mg (flat dose) Days 1-14 and romidepsin 14 mg/m^2 on Days 8, 15, and 22 on an every 35 day cycle. All patients receiving romidepsin will receive potassium and magnesium supplementation as recommended in the package insert of the product. In all cycles romidepsin will be administered first over 4 hours. Reported adverse events and potential risks for oral 5-azacitidine and romidepsin are described in Section 7. Appropriate dose modifications are described in Section 6. No investigational or commercial agents or therapies other than those described may be administered with the intent to treat the patient's malignancy.

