#### 5.1.4

#### Guidelines for Study Drug Administration

- Oral 5-azacitidine will be taken between the hours of 8 and 10 am daily (patient will be required to maintain a drug log recording side effects and time of dosage) on Days 1-14
- Romidepsin will be administered over 4 hours through either a peripheral or central venous catheter on Days 8, 15, 22 of a 35 day cycle. It will be administered within 6 hours of the oral dose. On the day of PK sampling in Cycle 1, the azacitidine will be taken with romidepsin. A dose of the anti-emetic will be administered in accordance with the package insert of romidepsin.
- Administration of the study drugs will be allowed within 48 hours of the scheduled dates.
- Missed doses will not be made up.

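### The Section 5.1.1 regimen table qualifies the Day 22 romidepsin infusion with an undefined plus-or-minus mark; every other statement of the Phase II starting regimen lists Day 22 without qualification

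*Combined protocol and SAP*

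**What the plan says.** Table 1 under Section 5.1.1 gives azacitidine 300 mg flat on Days 1-14, romidepsin 14 mg/m² over 4 hours and a 35-day cycle. Its romidepsin schedule cell reads "Days 8, 15, 22 (+/- D 22", followed by a closing bracket. The mark is not explained there or anywhere else. The footnote says "Doses as appropriate for assigned dose level".

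The other statements of the Phase II starting regimen carry no such mark:

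- Synopsis, table of the same title: "Days 8, 15 and 22". It has the same doses, cycle length and footnote.
- Synopsis, Phase II treatment plan: the same three days every 35 days.
- Schema for Phase II and the exploratory cohort: "on Days 8, 15 and 22 on a 35 day cycle".
- Section 5.1.2, headed as the Phase 2 regimen: "on Days 8, 15, and 22 on an every 35 day cycle".
- Section 5.1.4: "on Days 8, 15, 22 of a 35 day cycle".
- Table 2, Level 5, on a 35-day cycle: "14 (Days 8, 15 and 22".
- Section 2.4.2: the declared MTD has romidepsin on Days 8, 15 and 22 every 35 days.
- Section 10: the calendar marks romidepsin on Days 8, 15 and 22, in cycle 1 and in later cycles.

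Section 5.1.6 lets Phase II patients step down for recurrent Grade 3 toxicity, for Grade 4 toxicity, or at the physician's discretion. Each step it lists gives romidepsin on Days 8 and 15 of a 28-day cycle.

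**The concern.** Two tables with the same title, doses and cycle length disagree on whether the third infusion is fixed. The qualified copy is in the Treatment Plan, the section a prescriber would consult.

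Read as with or without, the cell permits a two-infusion cycle with no toxicity trigger and no modification rule. An omission on that basis could be logged as compliant, neither a deviation nor a dose reduction, and might not be identifiable in the exposure data. Section 5.1.4 says missed doses are not made up, so the infusion would not be recovered. Phase II is meant to evaluate the response rate at the MTD in 24 patients (Section 13.2), so the assigned starting schedule should be stated in one way only.

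**Working it through.** The plan gives no cumulative romidepsin dose per cycle, so there is no figure of its own to reproduce. The check has three steps.

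**1. Which dose level is the row?** The cell's row has azacitidine 300 mg on Days 1-14, romidepsin 14 mg/m² and a 35-day cycle. In Table 2 only Level 5 has all three, and it lists Day 22 outright. Level 6 shares the romidepsin dose and cycle length but gives azacitidine on Days 1-21. Levels -1 to 4 have no Day 22 and run on 28 days. A 35-day cycle with Day 22 left out therefore corresponds to no listed level.

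**2. Does other text explain the mark?**

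- *A visit window.* The cell gives no number of days. Sections 5.1.4 and 6.1 already allow 48 hours around scheduled drug dates, and the calendar carries a general note of plus or minus 3 days. Neither is confined to Day 22.
- *The footnote.* It speaks of doses. It also stands under the synopsis copy, which has no mark, so it does not account for the difference.
- *De-escalation.* Section 5.1.6 removes Day 22 but also shortens the cycle to 28 days. The cell keeps 35 days.

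**3. How much drug is involved?** Dose per cycle = infusions × dose per infusion. Weekly dose = dose per cycle ÷ cycle weeks.

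| Schedule | Dose per cycle (mg/m²) | Weeks | mg/m² per week |
|---|---|---|---|
| Level 3 | 2 × 10 = 20 | 4 | 5.0 |
| Level 4 | 2 × 14 = 28 | 4 | 7.0 |
| Level 5, Phase II regimen | 3 × 14 = 42 | 5 | 8.4 |
| Table 1 row without Day 22 | 2 × 14 = 28 | 5 | 5.6 |

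Day 22 supplies 14/42 = 33.3% of the cycle dose. In weekly terms, 1 − 5.6/8.4 is also 33.3%. The step down to Level 4 (called Cohort 5 in Section 5.1.6) lowers the weekly dose by 1 − 7.0/8.4 = 16.7%. An omission under the with-or-without reading would thus cut weekly dose twice as much as the first written de-escalation step.

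**The case against.** The strongest reply is that the mark is leftover text. The table sits under the dose-escalation heading, its footnote refers to an assigned level, and Phase I had levels both with and without Day 22, so the mark would suit a table once meant to cover them all. The same row looks dated elsewhere: it ties giving romidepsin first to cycle 1, whereas Section 5.1.2 says all cycles. The section written for Phase II gives one schedule, and no text sets a criterion for dropping Day 22 in a patient without toxicity. This stands as a likely origin, and it lowers the chance of misdosing. It does not remove the contradiction, because the row now carries the Phase II dose and cycle length.

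It is also fair to say that delivered infusions will vary anyway. Doses may be held for toxicity (Section 6.3.1), missed doses are not made up, and Section 5.1.6 allows reduction, including at the physician's discretion. So a Phase II patient without a Day 22 infusion is not in itself a departure from the plan.

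A reader might infer that the two-infusion version has no Phase I safety data behind it. The documents do not support that. Level 4 gives the same azacitidine and the same two 14 mg/m² infusions in cycle 1, repeated sooner, and DLT is essentially a cycle 1 measure (Section 5.2). Section 2.4.2 reports that escalation continued beyond that combination.

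**Conclusion.** The inconsistency is real and should be fixed. It is a fault in the document; nothing shows that anyone chose to make Day 22 optional.

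The size is up to one third of the romidepsin dose per cycle. That rests on two assumptions: that the mark means with or without, and that Day 22 is in fact omitted. The full third over a patient's treatment needs omission in every cycle. The documents give no basis for estimating how often that would happen.

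Two further inferences go too far:

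- *That the 24 patients would be a mixture and the response rate would not describe the MTD regimen.* The response rate describes the assigned starting regimen together with its modification rules. No effect on the 25% versus 50% comparison has been shown.
- *That different sites would follow different pages.* Section 13.1 describes Phase I as single-institution, and no text describes several Phase II sites. The risk lies with whoever prescribes from that table.

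This review does not say which schedule is right.

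**What to change.** Reconcile the romidepsin cell of Table 1 in Section 5.1.1 with the synopsis treatment plan and synopsis Table 1, the Phase II schema, and Sections 5.1.2, 5.1.4 and 5.1.6, so that one Phase II starting schedule is stated throughout. The choice of schedule belongs to the sponsor and the investigator. If Day 22 may be omitted, replace the mark with a reference to the written modification rule that allows it, and record each omission as a dose modification in the exposure data.

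The cost is one table cell in an amendment, plus a cross-reference and an entry in the dosing record if omission is to be permitted. Sample size, decision rules and analysis are unaffected.
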